## 11 APPENDICES

### 11.1 APPENDIX 1: FOLSTEIN MINI MENTAL STATUS EXAMINATION

Folstein Mini Mental Status Examination			
Task	Instructions	Scoring	
Date Orientation	"Tell me the date?" Ask for omitted items.	One point each for year, season, date, day of week, and month	5
Place Orientation	"Where are you?" Ask for omitted items.	One point each for state, county, town, building, and floor or room	5
Register 3 Objects	Name three objects slowly and clearly. Ask the patient to repeat them.	One point for each item correctly repeated	3
Serial Sevens	Ask the patient to count backwards from 100 by 7. Stop after five answers. (Or ask them to spell "world" backwards.)	One point for each correct answer (or letter)	5
Recall 3 Objects	Ask the patient to recall the objects mentioned above.	One point for each item correctly remembered	3
Naming	Point to your watch and ask the patient "what is this?" Repeat with a pencil.	One point for each correct answer	2
Repeating a Phrase	Ask the patient to say "no ifs, ands, or buts."	One point if successful on first try	1
Verbal Commands	Give the patient a plain piece of paper and say "Take this paper in your right hand, fold it in half, and put it on the floor."	One point for each correct action	3
Written Commands	Show the patient a piece of paper with "CLOSE YOUR EYES" printed on it.	One point if the patient's eyes close	1
Writing	Ask the patient to write a sentence.	One point if sentence has a subject, a verb, and makes sense	1
Drawing	 Ask the patient to copy a pair of intersecting pentagons onto a piece of paper.	One point if the figure has ten corners and two intersecting lines	1
Scoring	A score of 24 or above is considered normal.		30
Adapted from Folstein et al, Mini Mental State, J PSYCH RES 12:196-198 (1975)			

## **11.2 APPENDIX 2: NEUROLOGICAL FUNCTION CLASS**

1. Able to work and perform normal activities. Neurological findings minor or absent.
2. Able to carry out normal activities with minimal difficulty. Neurological impairment does not require nursing care or hospitalization.
3. Seriously limited in performing normal activities; requires nursing care or hospitalization. Patient confined to bed or wheelchair or with significant intellectual impairment.
4. Unable to perform even minimal normal activities. Requires hospitalization and/or constant nursing care. Patient unable to communicate or in a coma.

### 11.3 APPENDIX 3: ON-STUDY EVALUATIONS

Cycle/ Visit	H&P	Ophtho Exam	Toxicity Assess	MMSE	Clin. Labs	Cr. Cl.	Screen	MRI	PET	CSF	HIV/ CD4	EBV	Research Blood	Neuro- psych	Adherence
Cycle 1	X		X	X	X	X		X 	X 	X 	X 	X	X		
Cycle 2	X		X	X	X	X		X							
Cycle 3	X		X	X	X	X		X							
Cycle 4	X		X	X	X	X		X							
Cycle 5	X		X	X	X	X		X							
Cycle 6	X		X	X	X	X		X							
Cycle 7	X		X	X	X	X		X							
Cycle 8	X		X	X	X	X		X							
CR by MRI		X 						X							
End Rx	X	X 	X	X	X	X		X							
Follow-up															
Q2 mo x3															
Month 2	X		X		X	X		X							
Month 4	X		X		X	X		X							
Month 6	X		X		X	X		X							
Q3 mo x6															
Month 9	X		X		X	X		X							
Month 12	X		X		X	X		X							
Month 15	X		X		X	X		X							
Month 18	X		X		X	X		X							
Month 21	X		X		X	X		X							
Month 24	X		X		X	X		X							
Q6 mo x2															
Month 30	X			X			X		X						
Month 36	X			X			X		X						
Q12 mo x2 (Optional Clinical Follow up)															
Month 48	X			X						X					
Month 60	X			X						X					

1. Repeat if abnormal at baseline.

H&P= History and Physical, including ECOG; Ophtho Exam = Ophthalmology exam for orbital involvement; Clin. Labs = CBC with differential and Retic, Chem. 20, PT/PTT, Urine: UA,  $\beta$ -hCG (women); Cr. Cl. = estimated creatinine clearance by Cockcroft-Gault formula (Appendix 4); Serology = Hepatitis and Toxoplasmosis serologies, RPR; CSF = CSF cell count, glucose, protein, EBV, molecular pathology, flow cytometry ; HIV/CD4 = Baseline HIV Serology, genotype if indicated, HIV viral load, and lymphocyte subset TBNK; EBV = EBV quantitative PCR, blood; Neuropsych, See Appendix 5; Adherence, see Appendix 6. BL = Baseline Studies; End Rx = End of therapy, Cycle 8, Day 28 (Month 1 follow-up).  
 For patients that relapse, re-staging will include: MRI-brain with contrast, CNS FDG-PET, CSF studies, quantitative EBV-PCR, and ophthalmologic examination. See Section 3.8.5.

**On-Study Evaluations for Best Available Radiation Sparing Therapy (no Methotrexate)**

Cycle/ Visit	H&P	Ophtho Exam	Toxicity Assess	MMSE	Clin. Labs	Cr. Cl.	Serology	MRI	PET	CSF	HIV/ CD4	EBV	Research Blood	Neuro- psych	Adherence
Screen/BL	X	X			X	X	X	X	X	X	X				
Day 1	X		X	X	X	X					X	X			
Day 3	X		X	X	X	X			X						
Day 5	X		X	X	X	X									
Day 8	X		X	X	X	X									
Day 15	X		X	X	X	X									
Day 21	X		X	X	X	X									
CR by MRI			X 												
End Rx	X	X 	X	X	X	X		X	X	X	X	X	X	X	X
Follow-up															
Week 2	X		X	X	X	X									
Week 4	X		X	X	X	X									
Q2 mo x3															
Month 2	X		X	X	X	X									
Month 4	X		X	X	X	X									
Month 6	X		X	X	X	X									
Q3 mo x6															
Month 9	X		X	X	X	X									
Month 12	X		X	X	X	X									
Month 15	X		X	X	X	X									
Month 18	X		X	X	X	X									
Month 21	X		X	X	X	X									
Month 24	X		X	X	X	X									
Q6 mo x 2															
Month 30	X		X	X	X	X									
Month 36	X		X	X	X	X									
Q12 mo x2															
Month 48	X		X	X	X	X									
Month 60	X		X	X	X	X									

 Repeat if abnormal at baseline.

H&P= History and Physical, including ECOG; Ophtho Exam = Ophthalmology exam for orbital involvement; Clin. Labs = CBC with differential and Retic, Chem. 20, PT/PTT, Urine: UA,  $\beta$ -hCG (women); Cr. Cl. = estimated creatinine clearance by Cockcroft-Gault formula (Appendix 4); Serology = Hepatitis and Toxoplasmosis serologies, RPR; CSF = CSF cell count, glucose, protein, EBV, molecular pathology, flow cytometry; HIV/CD4 = Baseline HIV Serology, genotype if indicated, HIV viral load, and lymphocyte subset TBNK; EBV = EBV quantitative PCR, blood; Neuropsych, See Appendix 5; Adherence, see Appendix 6. BL = Baseline Studies; End Rx = End of therapy, Day 28 (Week 1 follow-up.)

For patients that relapse, re-staging will include: MRI-brain with contrast, CNS FDG-PET, CSF studies, quantitative EBV-PCR, and ophthalmologic examination.

## 11.4 APPENDIX 4: CALCULATION OF CREATININE CLEARANCE

### I. Calculation: Cockcroft-Gault formula for Creatinine Clearance (CrCl) estimate

- A. Male CrCl =  $(140 - \text{age}) \times (\text{weight}) / (\text{sCr} \times 72)$
- B. Female CrCl =  $(140 - \text{age}) \times (\text{weight}) \times 0.85 / (\text{sCr} \times 72)$
- C. Annotation
  - 1. Where creatinine clearance is expressed in mL/min
  - 2. Where age is in years
  - 3. Where weight is Actual Body Weight in kilograms
  - 4. Where sCr is Serum Creatinine in mg/dL
- D. Efficacy
  - 1. As accurate as CrCl measured from a 24-hour urine collection in many cases
  - 2. Exceptions: See 24-hour CrCl indications below
  - 3. For estimated creatinine clearance of <100 mL/min, a 24-hour urine collection should be obtained *plus* a serum creatinine at the end of the collection period to determine a measured creatinine clearance (per section 3.4.2.1.1).
- E. Resources: <http://www.kidney.org/professionals/>

### II. Calculation: Measured Creatinine Clearance from 24-hour urine collection

- A.  $\text{CrCl} = (\text{uCr} \times \text{uV}) / (\text{sCr} \times 1440)$
- B. Annotation
  - 1. Where CrCl is Creatinine clearance in mL/min
  - 2. Where uCr is Urine Creatinine in mg/dL
  - 3. Where sCr is Serum Creatinine in mg/dL
  - 4. Where uV is 24-hour urine volume in mL
  - 5. Where 1440 represents number of minutes in 24 hours
- C. Indications (where calculation above is inaccurate)
  - 1. Altered protein intake
    - a. Vegetarian diet
    - b. Creatine Supplementation
  - 2. Altered muscle mass and muscle injury
    - a. Malnutrition, muscle wasting, muscle trauma
    - b. Amputation
  - 3. Females
  - 4. Unstable renal function (changing serum creatinine)
  - 5. Obesity

## 11.5 APPENDIX 5: NEUROPSYCHOLOGICAL TEST BATTERY

At entry into the study, patients will be administered a comprehensive neuropsychological battery of tests. The major domains of functioning to be evaluated for the comprehensive and monitoring assessment batteries are indicated below. The specific tests to be used for the protocol will be selected by the NCI/MICC neuropsychology group. Such tests have been shown to provide an effective assessment of functioning in similar chronically ill populations. The tests do not require complicated instrumentation and can be done with high reliability and validity by trained personnel. Repeated neuropsychological assessments will be administered to the patient according to the schedule specified in the protocol. The monitoring battery, which may be administered at shorter intervals, includes tests less subject to practice effects. The same domains should be assessed using the same test instruments throughout the study.

### **Comprehensive Assessment**

- General Cognitive
- Language/Verbal
- Visual-Perceptual
- Processing Speed
- Memory (working, immediate and delayed, visual and auditory)
- Executive Function
- Attention
- Fine Motor
- Mood/QOL

### **Monitoring assessment**

- General Cognitive
- Language/Verbal
- Visual-Perceptual
- Processing Speed
- Working memory
- Executive Function
- Attention
- Fine motor
- Mood/QOL

--Additional neuropsychological tests may be administered to more comprehensively assess the patients if needed to further explore specific areas of functioning

--The comprehensive assessment is administered at baseline and then annually, whereas the monitoring assessment is administered at the half-year assessments.

## **11.6 APPENDIX 6: ADHERENCE ASSESSMENT**

Baseline, 6, and 12 months	Estimated Time
Knowledge Questionnaire	5 minutes
Pills Identification Test	5 minutes
Interview	10 minutes
	20 minutes total
Baseline, 3 and 9 months	
Interview	10 minutes
	10 minutes total

## 11.7 APPENDIX 7: KNOWLEDGE QUESTIONNAIRE

Hosp #:  
Name:

Protocol:  
Date:

**Please circle the best response for the questions below. Circle *one and only one* response for each question.**

1. HIV is a virus that:
  - a) can be cured with a vaccine.
  - b) cannot be controlled with medication.
  - c) can often be controlled with antiretroviral medicine taken the way it is prescribed.
  - d) can be controlled with antiretroviral medication in people who have received the vaccine.
  
2. It is important for people to take HIV medicine the way it is prescribed because this will help the body:
  - a) get a higher viral load.
  - b) build up resistance to the medicine.
  - c) keep a strong immune system.
  - d) all of the above.
  
3. Resistance means:
  - a) HIV resists the process of changing into AIDS.
  - b) immune cells fight with HIV cells.
  - c) HIV learns to grow even with medicine in the body.
  - d) HIV is killed by the medicine.
  
4. A measure of “viral load” tells us:
  - a) How many different viruses are in someone’s blood.
  - b) How many T-cells a person has.
  - c) How much HIV is in someone’s blood.
  - d) What kinds of HIV cells are in someone’s saliva.
  
5. If you run out of HIV medicine, you should:
  - a) schedule an appointment at NIH to get more.
  - b) call the nurse or doctor right away to get more.
  - c) borrow some pills from a friend until you can get more from the pharmacy.
  - d) both B and C are correct.
  
6. The best thing to have is:
  - a) high viral load and low T-cells.
  - b) low viral load and low T-cells.
  - c) high viral load and high T-cells.
  - d) low viral load and high T-cells.
  
7. The best way to fight HIV is:
  - a) take HIV medicines the way they are prescribed.
  - b) eat healthy foods.
  - c) get the HIV vaccine.
  - d) exercise every day.
  
8. Which of these statements is NOT true?
  - a) A person can only be resistant to one medicine at a time.
  - b) Doctors can do a test to see which HIV medicines work best for a person.
  - c) If you become resistant to a medicine, the medicine probably won’t work for you.
  - d) There are many different types or “strains” of HIV.
  
9. If a person doesn’t take his medicine every day,
  - a) the medicine will work better.
  - b) his red blood cells will be destroyed.
  - c) his T-cells will become resistant to the medicine.
  - d) the HIV will become resistant to the medicine.
  
10. If a person skips doses of her HIV medicine,
  - a) her viral load will probably go to zero.
  - b) she will probably gain weight.
  - c) her CD4 cells will probably double.
  - d) her body could become resistant to the medicine.

## 11.8 APPENDIX 8: RECRUITMENT ANNOUNCEMENT

**Clinical Trial for AIDS-related Primary Central Nervous System Lymphoma**  
**HIV and AIDS Malignancy Branch**  
**National Cancer Institute**  
**National Institutes of Health**  
**Bethesda, Maryland**

Individuals with AIDS-related primary central nervous system (brain) lymphoma are invited to participate in a clinical trial designed to study the feasibility of treating this cancer without using the radiation therapy approaches traditionally used in this setting. Patients are invited to contact the NCI if they are HIV-infected and have a brain mass, even if the diagnosis for the cause of the brain mass has not been made. In certain circumstances, the diagnostic procedures may also be done at the National Institutes of Health.

AIDS-related primary brain lymphoma is a serious and life threatening complication of HIV infection. Few individuals with this cancer survive for one year. Radiation therapy to the brain is the treatment commonly administered. Radiation therapy can make the lymphoma go away. However, many patients have recurrence of the lymphoma after radiation therapy, or develop other AIDS complications that limit survival. With the availability of highly active antiretroviral therapy, many individuals with AIDS-related primary brain lymphoma may be able to control the HIV infection long-term and go on to good health if the lymphoma can be cured. Many not HIV-infected people treated with radiation therapy for brain lymphoma survive several years, but have severe brain problems related to the radiation treatment. Therefore, in not HIV-infected people, chemotherapy has become the standard of care for treating this cancer. Survival with a healthy brain in such people is improved with this strategy. This clinical trial will assess whether chemotherapy will lead to several years or longer survival without brain problems in people with AIDS-related primary brain lymphoma.

The treatment being studied in this experimental trial is to give a combination of high-dose methotrexate, leucovorin, rituximab, and highly active antiretroviral therapy. This treatment is designed to treat the lymphoma without causing additional toxicity to the CD4+ lymphocytes. CD4+ lymphocyte recovery is essential for the long-term survival prospects of people with advanced AIDS. High-dose methotrexate is the core of most treatments for this tumor in HIV-unrelated primary brain lymphoma and it is used in that setting in conjunction with other medications. When given with leucovorin, high-dose methotrexate can usually be given without causing the expected toxicity to the bone marrow and to the immune system. Rituximab is being given because it is a monoclonal antibody that targets the lymphoma cells and helps the methotrexate kill the cancer cells. Since rituximab does not attach to the CD4+ lymphocytes, it may be possible to give methotrexate, leucovorin, and rituximab along with highly active antiretroviral therapy and simultaneously treat the cancer and the HIV. Some patients may not be able to receive high-dose methotrexate due to problems with their kidneys or heart. In such cases, treatment may still be possible, and will generally include rituximab and antiretroviral therapy. It may be possible to commence immune system recovery during

the lymphoma therapy. Immune system recovery may be essential not only to prevention of other AIDS complications, but also to prevention of recurrent brain lymphoma.

The study is designed to test the ability of this treatment to make the cancer go away, to see the extent of immune recovery that is feasible with the treatment, and to see whether the cancer comes back or not. Also, a series of tests will be done to measure the effects of this therapy on brain function, to see whether this therapy is less toxic to the brain than would be potentially expected with radiation therapy.

Frequent visits and prolonged stays at the NIH may be necessary since this disease is a very serious condition causing many complications. Each treatment will require a week or longer in the hospital. The treatments will be repeated up to 8 times depending on how well it is tolerated, and the effects on the tumor. All of the diagnostic tests and medical treatments administered at the National Institutes of Health are free of charge. If the cancer goes away, treatment for HIV may continue for up to three years while additional tests on your immune system and brain function are made.

Transportation costs to the NIH will be paid for those who do not live close to the NIH campus.

For further information about coming to the NIH for consultation and possible enrollment into this clinical trial, contact [name] at [contact], or [name], and then hit 4.

## 11.9 APPENDIX 9: RITUXIMAB COMBINED WITH HIGH-DOSE METHOTREXATE WITH LEUCOVORIN RESCUE HAART AND CHEMOTHERAPY ADMINISTRATION, METHOTREXATE MONITORING AND SUPPORTIVE CARE GUIDELINES

### Baseline/Admission:

1. Determine HAART regimen. Tenofovir sparing regimens preferred due to potential overlapping renal toxicity. Pharmacogenetic testing for abacavir; check HLA B\*5701
2. PCP prophylaxis; monthly pentamidine or atovaquone preferred
3. MAC prophylaxis: azithromycin 1200 mg /m^2 weekly for CD4 < 100 cells/microL
4. HSV prophylaxis: Valacyclovir 1000 mg/daily
5. Evaluate for thrush daily
6. Check Cockcroft-Gault estimate of creatinine clearance. If < 100mL/min, order 24 hour urine collection for creatinine clearance
7. Daily weights

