3.3.4 High-Dose Methotrexate with sodium bicarbonate followed by leucovorin rescue

3.3.4.1 Prior to HIGH-DOSE METHOTREXATE infusion, administer anti-emetic medication. Recommended: ondansetron 24 mg orally 1 hour prior to methotrexate, followed by ondansetron 8 mg orally every 8 – 12 hours for 3 days.

3.3.4.2 On day 2, after urine pH  $\geq 7.0$  and urine output  $>100$  mL/hour are confirmed, administer methotrexate  $6000$  mg/ $m^2$  IV over 4 hours (goal start time for methotrexate administration is 9AM – 10AM):

3.3.4.2.1 Administer methotrexate  $6000$  mg/ $m^2$  x 1 bottle with  $NaHCO_3$  25-75 mEq diluted in 5% Dextrose/0.45% Sodium Chloride Injection (qs.) 1000 mL at 250 mL/hour (i.e., over 4 hours).

3.3.4.2.2 Order daily serum methotrexate levels timed to start 24 hours after methotrexate administration begins and continue daily measurements until the serum methotrexate level is  $\leq 0.05$  mcMol/L.

3.3.4.2.3 Continue IV or oral hydration with urine alkalinization (pH  $\geq 7.0$  to  $\leq 8.0$ ) until serum methotrexate level is  $\leq 0.05$  mcMol/L (see sections 3.3.3.3 and 3.3.4.2)

3.3.4.3 **Leucovorin rescue**, starting 24 hours after methotrexate administration began (generally on day 3):

3.3.4.3.1 Administer leucovorin calcium  $100$  mg/ $m^2$  per dose IV (preferred) or levoleucovorin calcium  $50$  mg/ $m^2$  per dose IV every 6 hours until the serum methotrexate level is  $<0.5$  mcMol/L.

3.3.4.3.2 When the methotrexate level is  $<0.5$  mcMol/L, parenterally administered leucovorin or levoleucovorin may be replaced with leucovorin administered

orally (10 mg/m^2, or a fixed 25-mg dose for patients with BSA <2.5 m^2), until the methotrexate level is  $\leq 0.05$  mcg/L.

3.3.4.3.3 For patients with delayed methotrexate clearance, see sections 3.4.3 and 3.4.4.

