### 3.9.4 MAC prophylaxis

Essentially all patients on study will require prophylaxis since AR-PCNSL occurs in those with CD4+ cells <50/mm^3.

Azithromycin 1200 mg orally once weekly is recommended, but other agents are

acceptable.

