Additionally, up to 10 additional patients who are not eligible to receive high-dose methotrexate may be accrued in the “Radiation-sparing Best Available Care” Cohort. The patients enrolled in this limited size cohort will be evaluated for the same endpoints as in the main cohort receiving high-dose methotrexate, but given the limited number of patients who will enroll into this cohort, all analyses in this cohort will be considered hypothesis generating and exploratory. Accrual to this cohort will close when 15 evaluable patients have been enrolled in the main cohort.

All secondary endpoints will be evaluated using explorative techniques, and will be reported as exploratory, since the study is not designed to address any of these points with more than minimal power.

Since part of the treatment strategy is aimed at HIV suppression and immune reconstitution, up to 3 patients who are non-adherent with HAART within the first 9 months of therapy may be replaced. It can often take up to 9 months to adjust medications for purposes of optimizing medication tolerance and adherence to antiretroviral therapy. Patients who are clearly non-adherent and thus are unable to maintain an HIV viral load of <5000 copies HIV mRNA/mL plasma and do not have an increment in the CD4+ cells to above 75/mm^3 by the end of 9 months may be replaced. Patients who maintain lower HIV viral loads but do not have adequate immune recovery will not be replaced, and will be considered treatment failures in the event of tumor recurrence. Informal comparison will be made between those who are HAART naive at entry and those who are antiretroviral experienced.

This is a rare condition, and it is expected to take between 6 and 10 years to enroll 15 patients onto this trial in the main cohort and up to 10 in the cohort not receiving high-dose methotrexate. Up to three patients may be replaced if during the first 9 months they are clearly non-adherent with HAART as described above. Thus an accrual ceiling of 28 patients will be used.

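### Appendix 9 gives weekly azithromycin prophylaxis per square metre of body surface; section 3.9.4 gives the same number of milligrams as a flat dose

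*Combined protocol and SAP*

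**What the plan says.** Section 3.9.4 (MAC prophylaxis) states that "Azithromycin 1200 mg orally once weekly is recommended". It leaves room for alternatives: the dose "is recommended, but other agents are" acceptable. It also says who needs prophylaxis: "Essentially all patients on study will require prophylaxis since AR-PCNSL occurs in those with CD4+ cells <50/mm" (cells per cubic millimetre).

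Appendix 9 is the step-by-step guide to giving rituximab with high-dose methotrexate, and its title includes supportive care. Item 3 of its Baseline/Admission list begins "MAC prophylaxis: azithromycin 1200 mg /m"; in full it reads "MAC prophylaxis: azithromycin 1200 mg /m 2 weekly for CD4 < 100 cells/microL". The next item in the same list is "HSV prophylaxis: Valacyclovir 1000 mg/daily".

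Section 4.4.2 names azithromycin for treating established MAC infection but gives no dose. No other section gives an azithromycin dose.

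**The concern.** Drug, indication, frequency and number of milligrams are the same in both places. Only the unit differs: flat in section 3.9.4, scaled to body surface in Appendix 9. For any adult with a BSA above 1.0 m², the two instructions give different doses.

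This is a dosing line in a working checklist for use at admission, and section 3.9.4 expects almost every patient to need MAC prophylaxis. The appendix line does not point to section 3.9.4, states no route, and does not mention that other agents may be used. Someone working only from the checklist would have no prompt to notice the conflict. It is also unclear which dose complies with the protocol, although section 8.1.8 counts any departure from the approved text as a deviation and section 8.2.1 asks for all deviations to be reported.

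What is at stake is the safety and consistency of supportive care. No estimate or test in section 6 depends on it.

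**Working it through.** **Can the two texts be reconciled?**

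| | Section 3.9.4 | Appendix 9, item 3 |
|---|---|---|
| Amount | 1200 mg, flat | 1200 mg per m² |
| Frequency | weekly | weekly |
| Route | oral | not stated |
| CD4 wording | below 50, describing the study population | below 100, as a threshold |
| Alternatives | allowed | not mentioned |

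The CD4 wording does not separate two groups of patients. A patient below 50 is also below 100, so the typical study patient falls under both instructions. Section 3.9.4 allows a different agent, but it does not offer a per-square-metre azithromycin dose. The texts therefore conflict.

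**Which is the likely error?** The other antimicrobial prophylaxis doses in the protocol are flat:
- dapsone, pentamidine and atovaquone (section 3.9.3);
- levofloxacin (section 3.9.5);
- lamivudine and tenofovir for hepatitis B (section 3.9.6);
- valacyclovir (Appendix 9, the item directly below).

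Appendix 9 otherwise uses doses per square metre for rituximab, methotrexate and leucovorin. A unit carried over from those lines is a plausible explanation. This is an inference, so a clinician should confirm it.

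**Size of the discrepancy.** The appendix dose is 1200 mg/m² × BSA, and the ratio to section 3.9.4 is (1200 × BSA) / 1200 = BSA. The documents give no patient BSA, so the values below are assumptions.

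| Assumed BSA (m²) | Appendix 9 weekly dose (mg) | Excess over 1200 mg (mg) | Ratio |
|---|---|---|---|
| 1.5 | 1200 × 1.5 = 1800 | 600 | 1.5 |
| 1.8 | 1200 × 1.8 = 2160 | 960 | 1.8 |
| 2.0 | 1200 × 2.0 = 2400 | 1200 | 2.0 |
| 2.2 | 1200 × 2.2 = 2640 | 1440 | 2.2 |

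The only BSA value near this range in the protocol is the cut-off for oral leucovorin in section 3.3.4.3.2, "or a fixed 25-mg dose for patients with BSA <2.5 m" (square metres). At 2.5 m² the appendix dose would be 1200 × 2.5 = 3000 mg. That value is a dosing cut-off and not a typical patient, so the conclusion does not rest on it.

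**Number of patients under the appendix.** Section 6.1.3 plans 15 evaluable patients in the methotrexate cohort and up to 3 replacements: 15 + 3 = 18. This agrees with the overall limit, "Thus an accrual ceiling of 28 patients will be used", less the up to 10 patients in the cohort not given methotrexate: 28 − 10 = 18. Appendix 9 is titled for the methotrexate regimen, so those 10 are not dosed from it.

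**The case against.** The strongest reply concerns importance. Azithromycin here is supportive care, not study treatment. Neither place makes the dose mandatory: section 3.9.4 recommends it, and the title of Appendix 9 calls its contents guidelines. The documents contain no azithromycin toxicity data, and the drug is not on the protocol's list of medicines to avoid with methotrexate (section 3.9.7 and the end of Appendix 9). Appendix 9 ties order sets to the hydration fluids and to methotrexate but describes none for azithromycin. The documents therefore do not show how such an order is built or checked, and an actual overdose is not demonstrated.

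Most of this stands. It limits the point to a correction that should be made and rules out any claim of documented harm. It does not remove the conflict. Permission to use another agent does not license a different azithromycin dose, and a protocol should not depend on a pharmacist noticing the unit.

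A further objection also stands: 18 is a planned number, not a firm maximum. The target is 15 evaluable patients who receive all treatment, so patients who start but do not complete methotrexate may not count towards it. The 10 places in the other cohort are a ceiling and not a reservation.

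**Conclusion.** The inconsistency is real. Followed literally, Appendix 9 gives 1.5 to 2.2 times the weekly azithromycin dose in section 3.9.4, or 600 to 1440 mg more per week, if BSA lies between 1.5 and 2.2 m². That range is an assumption. About 18 planned patients in the methotrexate cohort are covered by the appendix, and some may receive another agent. That the appendix holds the error is well supported by the flat dosing elsewhere, but it is not proved. The primary endpoint, sample size, power and analysis are unaffected. The line should be corrected because it is a patient dosing instruction.

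**What to change.** After clinical confirmation, delete the per-square-metre unit from Appendix 9, Baseline/Admission, item 3, so that it gives a flat azithromycin dose of 1200 mg by mouth once a week, as section 3.9.4 does. A cross-reference to section 3.9.4 in the same line would also carry over the permission to use other agents. The cost is a one-line text amendment, with no change to the design, data collection or analysis.
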